- **Inspiratory Muscle Training:** HF patients have also been demonstrated to have reduced inspiratory muscle strength and endurance that exacerbates dyspnea³⁸ and exercise intolerance. Inspiratory muscle strength correlates with VO_2 in HF and is an independent predictor of survival^{39,40}. IMT has been demonstrated to improve the respiratory muscle metaboreflex as well as many of the pathophysiologic manifestations of HF. Quality of life, heart rate, respiratory rate, peak VO_2 , 6 minute walking distance, minute ventilation (VE), breathing efficiency (the VE/VCO_2 slope) and oxygen uptake efficiency slope (OUES), and recovery oxygen kinetics have all been shown to significantly improve after IMT in HF patients⁴¹⁻⁵¹. In one study Dall'Ago et al showed maximal inspiratory pressure increased 115% in the IMT group with 17% improvement in peak VO_2 and 19% improvement in 6MWT distance⁴². However within this literature, there is no research indicating the impact of IMT training on central mechanisms (cardiac reverse remodeling and/or changes in systolic/diastolic function). It should be noted the current proposal intentionally excludes patients with HF with preserved ejection fraction (HFpEF) as the clinical utility of IMT for HFpEF have not been established, and studying cardiac remodeling with IMT in this group is premature.

In summary this proposal evaluates central cardiac changes with exercise training in HF patients. Furthermore, it adds to the literature by comparing two training modes (IMT and aerobic training) verses controls. IMT is a novel exercise regimen that facilitates high intensity training of the diaphragm. Prior research has demonstrated systemic benefits akin to more traditional exercise training. In this study we will compare IMT to standard aerobic training to assess clinical benefits, but even more importantly on remodeling, diastole and systole, and the relative differences on central and peripheral mechanisms of disease. We expect IMT to be non-inferior compared to aerobic training in its benefits and in addition will have certain advantages over traditional aerobic training because it will not be restricted by notorious musculoskeletal limitations that so frequently encumber exercise-training goals in HF patients, who are typically old, deconditioned and limited by other morbidities and pain.

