As part of the VA MERIT F0834-R	Exercise Training	12 weeks	2-3 times a week of exercise training
At time of the third visit for VA MERIT F0834-R	Post assessment		echocardiographic

Recruitment

- Study Population:** 75 male and female HF patients with mild-moderate symptoms while on optimal medical therapy will be enrolled. The data collected from this pilot study will be used for building future research. HF diagnosis will be contingent on a previous hospitalization for HF or physician assessment of HF associated with either systolic or diastolic dysfunction, or on left ventricular ejection fraction $\leq 45\%$ in the absence of a physician diagnosis of HF (i.e., AHA stage B heart failure). Each candidate will be examined at the time of enrollment by a physician and/or cardiologist to ensure that he/she is clinically stable.

Inclusion Criteria: (a) NYHA class II or III or AHA Stage B or C with reduced ejection fraction ($\leq 45\%$), or AHA Stage C HF with preserved ejection fraction despite a minimum of 6 weeks of optimal treatment. (b) Age ≥ 50 years. (c) Optimal therapy according to AHA/ACC and HFSA HF guidelines, including treatment with an ACE

Inhibitor (or an angiotensin receptor blocker) and beta-blocker therapy (for at least 6 weeks), or have documented reason for variation, including medication intolerance, contraindication, patient preference, or personal physician's judgment.

Exclusion Criteria: (a) Major cardiovascular event or procedure within the prior 6 weeks. (b) Dementia. (c) Severe COPD (FEV1<50%), PVD that would limit exercise. (d) End-stage malignancy. (e) HF secondary to significant uncorrected primary valvular heart disease (except mitral regurgitation secondary to LV dysfunction and asymptomatic aortic regurgitation) (g) Orthopedic exercise limitation. (h) Women who are pregnant, breastfeeding, or likely to become pregnant within the next 6 months. (i) Psychiatric hospitalization within the last 3 months. (j) valve replacement or repair in past 12 months, (k) Chronic ETOH or drug dependency.

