Randomization will be generated using a SAS program based upon permuted random blocks of variable size to assure approximate balance over time and will be stratified by sex and statin use.

Aim 1a: *a) We hypothesize that exercise training will result in a decrease in Left ventricular end diastolic and end systolic volume and increase in ejection fraction (measures of morphology and systolic performance) as compared to the control group. b) We hypothesize that exercise training will increase mitral annular early diastolic velocity (e') as well as decrease the ratio (E/e') of early mitral inflow velocity (E) and e' (measures of diastolic performance). c) We hypothesize that both forms of training will be more beneficial compared to the control group and IMT will be non inferior to aerobic training regimen as related to cardiac remodeling.*

The outcomes for these hypotheses will be the outcome measures at baseline and at the end of follow-up. Parts a & b involve superiority tests using a mixed linear regression model comparing each active treatment group to the control group, specifically the interaction between time and treatment, with the ability to adjust for baseline values of the outcomes. Part c requires a test of non-inferiority between the two active treatments also involving a mixed model with a lower bound of 0.65 standard deviation units for each measure [see Sample Size and Power below].

Aim 2. *To explore the benefits of improved cardiac remodeling and physiology on functional and qualitative exercise training endpoints. a) We hypothesize that exercise training related cardiac improvements will lead to improved aerobic functional parameters (measured as peak VO_2 and VE/VCO_2 slope). b) We hypothesize that exercise training-related cardiac improvements will lead to improved quality of life.*

For hypotheses a & b, baseline and follow-up in peak VO_2 , VE/VCO_2 slope and quality of life will be the outcomes in separate mixed linear regression models using the measures of morphology, systolic and diastolic performance at evaluation times that were used as outcomes in aim 1 as predictors.

Exploratory Aim. Using the outcomes from aim 2 in separate mixed linear regression models using the predictors from aim 1 with the addition of potential confounders of peripheral function as determined by the supporting funded Merit to. We will evaluate the independent effect of central cardiac change on function.

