individuals with approval from the PI to access the data. Individuals must be properly credentialed research staff and must be compliant with VA security trainings (i.e., Research Data Security, HIPAA and VA Privacy Training, Cyber-Security, and Good Clinical Practices).

Dissemination and/or Implementation Plan: The findings of this study will be of key interest in a variety of scientific and clinical venues. Abstracts and associated manuscripts will target the Echocardiography, HF, and exercise research communities. Initial presentations/publications will include orientation to cardiac remodeling effects with focus on the overall mechanism of exercise induced clinical benefits and the relative contribution of central and peripheral effects with the 2 training modalities. We will also report on the role of exercise training modalities and their impact on heart failure management, issues of likely interest to HF and cardiac rehabilitation physicians. [name] and her team of investigators will participate in related meetings, particularly the American Heart Association (AHA). Drs. [name], [name], and [name] already regularly participate in the AHA/ACC/AHA as part of their careers. Likewise, the investigators participate in the American College of Sports Medicine, the HF Society of America and other laudable venues as part of their careers. Dissemination of the data/conclusions from this study will flow from these preexisting patterns.

Limitations: The goal to recruit 75 systolic HF patients, inclusive of men, women, and minorities is an inherent challenge for a two year proposal. We are confident we can achieve this because of the significant and well-organized initiatives we established within the VABHS (as part of previous pilot studies) to identify suitable candidates. A related limitation is the potential attrition of patients over an extended training trial. Illness and/or life stresses can potentially exacerbate attrition. [name] developed considerable experience with these types of dynamics in HF-ACTION (a large training trial in which there was only 5% attrition), and he will work closely with the study team to maintain subjects' adherence. Financial incentives will be helpful, but it became clear in HF-ACTION that the PI was the most important factor in maintaining patient participation. Steps will also be implemented to sustain participation in the event of illness, accidents, or travel.

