Patients can also dilute the training effects if they modify their regimen by doing supplemental exercises at home (e.g., adding aerobic exercises by those in the IMT arm of the study). We will emphasize the priority of maintaining precise training regimens, and will offer patients the chance to cross-train as soon as the formal protocol is completed.

Although the current proposal employs well-validated exercise training parameters^{3,40-43, 68}, it is possible that the duration and intensity of the exercise training (either IMT or aerobic) may not be adequate to induce measurable changes in cardiac geometry and or to systolic and diastolic physiological performance.

Human Subjects

A. Risk to Subjects

A. Human Subjects Involvement and Characteristics

The study population will consist of 75 male and female participants age 50 and older who have been diagnosed with systolic heart failure (HF). Recruitment will include only Veterans and will focus on the VA Boston Healthcare System for recruitment. All patients must be cleared by their physician to participate in a supervised exercise environment.

As indicated in the Methods section:

Inclusion Criteria

- NYHA class II or III or AHA stage B or C HF with reduced ejection fraction (≤ 45), or AHA stage C with preserved ejection fraction despite a minimum of 6 weeks of optimal treatment
- Age ≥ 50 years

- Optimal therapy according to AHA/ACC and HFSA HF guidelines, including treatment with ACEI and beta-blocker therapy (for at least 6 weeks), or have documented reason for variation, including medication intolerance, contraindication, patient preference, or personal physician's judgment.
- ✓ Patients using statins will be enrolled; in the pilot study it was evident that most patients eligible for this study were on statins since prevalence of hypercholesterolemia is high and most clinicians are attentive to prescribing statins as part of their standard of care. While this is potentially a confounding issue, we will be certain that statin use is balanced in each arm.

Exclusion Criteria

- Major cardiovascular event or procedure within the prior 6 weeks.
- HF secondary to significant uncorrected primary valvular disease (except mitral regurgitation secondary to left ventricular dysfunction). If valve replacement has been performed, patient may not be enrolled for 12 months after this procedure.
- Dementia
- Severe COPD (FEV1<50%),
- PVD that would limit exercise- End-stage malignancy

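### Eligibility contradicts itself on preserved ejection fraction: the rationale says these patients are deliberately left out, while both inclusion lists admit them, and no EF group appears in the strata or the Aim 1 model.

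*Combined protocol and SAP*

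**What the plan says.** All references are to the combined protocol and SAP.

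**Text that keeps HFpEF out**
- The inspiratory muscle training part of the section on rationales for the training modalities states that "the current proposal intentionally excludes patients with HF with preserved ejection fraction (HFpEF"). The reason given is that the usefulness of IMT there is not established and that "studying cardiac remodeling with IMT in this group is premature".
- Limitations: "The goal to recruit 75 systolic HF patients".
- Human Subjects, opening description: participants "who have been diagnosed with systolic heart failure (HF").

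**Text that lets HFpEF in**
- Recruitment, inclusion criterion (a): "or AHA Stage C HF with preserved ejection fraction despite a minimum of 6 weeks of optimal treatment".
- Human Subjects, first inclusion bullet: "or AHA stage C with preserved ejection fraction despite a minimum of 6 weeks of optimal treatment". This section therefore disagrees with its own opening description.
- Recruitment, diagnosis rule: a "physician assessment of HF associated with either systolic or diastolic dysfunction" qualifies, and so does a previous HF hospitalisation, with no EF limit attached.

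Neither exclusion list mentions preserved EF. Randomisation is stratified by sex and statin use. The Aim 1 model tests time by treatment and allows adjustment for the baseline value of the outcome. EF group is not mentioned in either place.

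**The concern.** The criteria decide who is enrolled, not the background section. The study is offered to Merit participants after their Merit baseline visit, and no EF screen is described at that step. Patients whom the rationale calls premature to study can therefore be enrolled without any protocol deviation.

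Three things are at stake.

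1. **The population cannot be stated.** A reader cannot tell whether the results describe systolic HF or HF in general.
2. **The systolic hypotheses may be diluted.** Aim 1 predicts a "decrease in Left ventricular end diastolic and end systolic volume and increase in ejection fraction (measures of morphology and systolic performance"). If patients whose EF is already preserved respond less on these measures, the average effect shrinks in a comparison that has no power to spare.
3. **The EF mix may differ between trained and control patients.** The 60 trained patients come from the Merit study. The 15 controls are recruited separately through flyers, mailings and clinics. Nothing in the design balances EF between the two sources, and the only analytic protection is an optional, outcome-specific baseline adjustment.

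**Working it through.** **1. The texts side by side**

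| Place | Preserved EF |
|---|---|
| Rationale for IMT | excluded on purpose |
| Limitations | systolic HF only |
| Human Subjects, description | systolic HF only |
| Recruitment, diagnosis rule | systolic or diastolic dysfunction; prior hospitalisation with no EF limit |
| Recruitment, inclusion (a) | admitted if AHA Stage C |
| Human Subjects, inclusion list | admitted if AHA stage C |
| Both exclusion lists | not named |

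No statement elsewhere gives one version precedence.

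**2. The plan's own power figure**

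Inputs from Sample Size and Power: 30 active, 15 control, alpha 5%, detectable difference 0.91 SD, power 80%. The plan does not say whether the test is one- or two-sided; a two-sided t-test matches.

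- Degrees of freedom: 30 + 15 − 2 = 43; critical t = 2.017.
- Noncentrality: d / √(1/30 + 1/15) = 0.91 / 0.3162 = 2.878.
- Power from the noncentral t distribution: 80.3%. The difference giving exactly 80% is 0.906 SD.

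The stated figure reproduces, so the power arithmetic is not in error.

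**3. Illustration of dilution, systolic measures only**

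Assumptions that are not in the documents: the true effect in reduced EF equals 0.91 SD; a share q of patients has HFpEF, equal in both arms; their response is a fraction r of the reduced-EF response; the SD is unchanged. Then

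d = 0.91 × [1 − q(1 − r)],

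with power computed as in step 2.

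| q | r = 0: d, power | r = 0.5: d, power | r = 1: d, power |
|---|---|---|---|
| 0% | 0.91, 80.3% | 0.91, 80.3% | 0.91, 80.3% |
| 10% | 0.82, 71.6% | 0.86, 76.2% | 0.91, 80.3% |
| 20% | 0.73, 61.4% | 0.82, 71.6% | 0.91, 80.3% |
| 30% | 0.64, 50.4% | 0.77, 66.7% | 0.91, 80.3% |
| 50% | 0.46, 29.0% | 0.68, 56.0% | 0.91, 80.3% |

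Example for q = 30%, r = 0: d = 0.91 × 0.70 = 0.637; noncentrality 0.637 / 0.3162 = 2.014; power 50.4%.

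**4. Power of an analysis restricted to LVEF ≤45%**

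With 30% HFpEF and no replacement, 30 × 0.7 = 21 trained and 15 × 0.7 = 10.5 control patients remain on average. Noncentrality is 0.91 / √(1/21 + 1/10.5) = 2.408 with 29.5 degrees of freedom, giving about 64% power at 0.91 SD. Whole numbers give 63% (21 vs 10) or 66% (21 vs 11).

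**The case against.** The strongest reply grants the contradiction and disputes what is built on it. Much of that reply stands.

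- **A reader might infer that the trial is powered for a systolic effect which HFpEF patients would dilute.** The documents do not support this. The 0.91 SD is one generic detectable difference for all of Aim 1, which includes e' and E/e', and the background makes diastolic remodelling a deliberate focus. It is also not presented as an expected effect. No dilution is shown for the diastolic measures.
- **A reader might take the zero-response column as the likely loss.** The documents give neither the HFpEF share nor its response, so that column is one end of a range whose other end is no loss.
- **A reader might infer that mixing EF groups widens the SD.** The test concerns change over time, and patients who change little may also vary less. The direction is undetermined.
- **A reader might infer that non-inferiority becomes too easy to pass.** That would be an error only if IMT were truly worse than aerobic training. The plan assumes a true difference of zero.
- **A reader might infer that HFpEF patients will enter.** The EF mix of the Merit study is not given, so only "can enter" is supported.
- **Stratifying by EF would not have balanced trained against control patients.** Randomisation is between IMT and aerobic training within the Merit study, and the controls come from outside it. The optional baseline adjustment also covers EF when EF is the outcome.

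None of this removes the contradiction. It stands even if dilution is zero.

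**Conclusion.** The point holds as an internal inconsistency in the eligibility rule. The rationale and the population descriptions exclude HFpEF, the operative criteria admit it, and nothing in the documents settles which is intended. It should be resolved even in a pilot, because it determines whom the results describe.

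The statistical consequence is conditional. Under the assumptions in the working, power for the systolic measures lies between 50% and 80% at 30% HFpEF, and between 29% and 80% at 50%, depending on how far HFpEF patients respond. The possible imbalance in EF mix between trained and control patients follows from the two recruitment routes, but its size cannot be estimated from the documents. The reproduced 0.91 SD figure is unaffected.

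**What to change.** The sponsor should state which population is intended and reconcile the IMT rationale, the Recruitment diagnosis rule, both inclusion lists, Limitations and the Human Subjects description. The documents do not show which version is right, so both routes are set out.

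**If HFpEF is meant to be excluded.** Both inclusion lists and the diagnosis rule must carry the same EF limit. Removing the preserved-EF clause alone is not enough. The NYHA wording can be read as free of the EF limit, and the prior-hospitalisation route has none. Cost: protocol wording, a smaller pool of Merit patients and slower accrual.

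**If HFpEF is meant to be included.**
- Correct the rationale, Limitations and Human Subjects statements.
- Keep the intent-to-treat analysis of all patients, with baseline EF group (≤45% vs preserved) as a covariate in every Aim 1 model. This addresses imbalance but does not restore a diluted effect.
- Report LVEDV, LVESV and EF in the LVEF ≤45% subset as a prespecified supporting analysis, and state its lower power: about 64% at 0.91 SD if 30% of patients have HFpEF.

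Cost: protocol wording, a short addition to Statistical Analysis, and one model term in a small sample.
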